The progressive accumulation of Gb-3 and its deacylated form lyso-Gb-3 creates an inflammatory environment (Figure 1). Furthermore, the accumulated Gb-3 and lyso-Gb-3 have been released into the cellular milieu from the ruptured lysosomes, leading to cell damage (2). Naturally sequestered inside live cells, these molecules are passively released extracellularly upon cell death and loss of membrane integrity. The elevated levels of both molecules in plasma and urine correlate with the impact of Fabry disease and may correspond to the short-term response to therapy with the reversal of cellular apoptosis.

Cells can die through several different mechanisms. Two of the significant types of cell death are necrosis and apoptosis. Sphingolipids are associated with apoptosis, where cells die while maintaining the integrity of their plasma membrane but are ingested by the tissue macrophages, in turn releasing pro- or anti-inflammatory signals such as TGF-beta or IL-10 (3). In contrast, necrotic cell death occurs in response to an insult such as infection and is associated with rapid loss of cell membrane integrity. Pyroptosis is a form of necrotic cell death due to a pro-inflammatory response (4). This pathway is uniquely dependent on Caspase-1, which is not involved in apoptotic cell death. Caspase-1 activation in macrophages results in the processing of Il-1 β with subsequent activation of the transcription factor NF- κ B.

The transcription factor NF- κ B regulates multiple aspects of immune functions and serves as a pivotal mediator of inflammatory responses (5). NF- κ B controls the expression of pro-

inflammatory cytokines (e.g., IL-1, IL-6, IL-8, and TNF α), chemokines (e.g., MIP-1, MCP1, RANTES, and Eotaxin), and vascular adhesion molecules (e.g., ICAM1, VCAM1, and E-selectin). NF- κ B is also a central mediator of TGF- β 1, the pathway central to the progression of fibrosis in multiple organs.

The responses induced by cell injury can cause significant damage while trying to heal the injured tissue. This is one of the reasons why it's important to elucidate these molecules in the urine not only to understand the order of pathogenic events associated with renal injury but also potentially block the cellular triggers of inflammation. Thus, this proposed study of pivotal urinary biomarkers may offer further insight on renal injury beyond current diagnostic tests.

[figure not shown]

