Common clinical biomarkers related to FD nephropathy (alpha-1-microglobulin, microalbumin, creatinine) will be compared with the pivotal biomarkers associated with the inflammatory and dysregulated immune pathways.

Table 2: Suggested pivotal biomarkers and pathways involved in Fabry nephropathy:

	Relationship to pathway or involvement	Biomarkers	
Inflammatory biomarkers	Cytokines	NF- κ B pathway	IL-1 β , IL-6, TNF- α , IL-10
		TGF- β 1 pathway	TGF- β 1, IL-4, INF-gamma
		TLR4 pathway	IL-18, IL-12
	Chemokines	NF- κ B pathway	MCP1, IL-8, RANTES, BAFF , APRIL
		TLR4 pathway	PAI-1
Biomarkers of kidney function and proteinuria	clinical laboratory urine biomarkers	alpha-1-microglobulin, albumin, cystatin C, GFR	
	We will measure in our laboratory	B2M, bikunin, NGAL, osteopontin, clusterin, creatinin.	
Acute kidney injury	Marker of renal tubular injury	KIM-1	
	Inflammation-associated glycoprotein	YKL-40	
	Growth factor, fibrosis	EGF	
	Apoptotic marker	CK-18 M30	
	Pyroptotic markers	IL-1β, IL-18 (included in the list of cytokines)	

This is a study to assess the markers related to autophagy, apoptosis, pyroptosis, and inflammatory markers related to NFkB, TNF-alpha, and TGF-β1 pathways in the urine. Urinary biomarkers will then be compared to the standard measures of kidney function and proteinuria: GFR, cystatin-C, B2M, bikunin, NGAL. Gb3 and Lyso-Gb3, urine microalbumin, and urine protein-to-creatinine (UPCR) ratio. We will also analyze the role of therapy, especially for the inflammatory responses in patients on stable enzyme replacement therapy (ERT) with that of patients naïve to therapy.

OBJECTIVE AND SPECIFIC AIMS

Primary objective: Identify biomarkers in urine for the detection and progression of kidney involvement in naïve male and female patients with FD, and compare with patients on ERT to assess the effects of ERT.

Specific Aims:

- 1) *To identify urinary inflammatory biomarkers associated with nephropathy in FD.*
- 2) *Analyze the association between urinary inflammatory markers, clinical urine biomarkers, circulating lyso-Gb3, and kidney involvement in naïve FD patients.*
- 3) *Analyze the association between urinary inflammatory markers, clinical urine biomarkers, circulating lyso-Gb3, and kidney involvement in FD patients on stable ERT.*

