This prospective study aims to establish novel biomarkers for non-invasive detection of kidney involvement in FD. FD patients will be assessed using the definition of Kidney Disease Outcomes Quality Initiative (KDOQI) 2002. The patients with CKD stages 3 or less with a progressive decline in kidney function, as evidenced by a decreasing GFR and a slope of less than -1.5, will be further assessed.

The glomerular filtration rate will be calculated from serum creatinine (CKD-EPI). The UPCR will be used to measure proteinuria. Additionally, the patients will be stratified as having low renal involvement (LRI) if the UPCR is less than or equal to 0.5 g/g. Anti-drug antibody status and other adverse events, such as the occurrence and the progression of cardiomyopathy as evidenced by LVMI, LVPWD, and neurological events such as strokes, will be recorded through the study. The categorization of kidney involvement via renal biomarkers will be defined (Table 4).

Table 4. Clinical staging of FD patients:

Clinical parameter(s)	FD patients and kidney involvement				Age-matched controls
	Stage 1	Stage 2	Stage 3a	Stage 3b	
Kidney involvement					
Kidney damage	Normal/	Mild reduction	Moderate reduction	Moderate reduction	Normal
GFR ml/min/1.73 m ²	>90	60-89	45-59	30-44	90 min
Cystatin-C	0.5-0.9	1.0-1.2	1.3-1.5	1.4-1.9	0.5-0.9
Urine B2M	-	0.428-0.603	0.603-0.950	0.950-1.034	-
FD biochemical markers					
α-Gal A	Deficiency	Deficiency	Deficiency	Deficiency	Normal
GLA mutations	Yes	yes	yes	yes	No
Gb-3	Yes	yes	yes	yes	No
Lyso-Gb-3	Yes	yes	yes	yes	No

The study will take place over 24 months. The clinical part of the active study to collect clinical data and the samples will be over 12 months. The urine samples will be collected three times (0, 6, and 12 months) (Table 5). A physical examination will be performed during the visits, and samples will be collected. We will review medical records as a part of the clinical evaluation. After a urine specimen collection, samples will be aliquoted and stored at -80⁰ C until biomarkers are screened. We expect to recruit the subjects within 6 months of the study initiation; thus, the last visit for the last subject is expected to be 19 months after the study starts.

Table 5. Visit and assessment schedule:

visits	baseline		
	1	2	3
	month 1/ enrollment	month 6	month 12
Vital signs	X	X	X
Height and weight	X		X
Physical examination	X		X
Concomitant medications	X	X	X
Adverse event reporting	X	X	X
Informed consent form	X		

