Events/issues which are part of the study objectives or endpoints will be systematically identified and collected from healthcare records or other applicable source records and summarized as part of any interim analysis and in the final study report. Such events do not need to be notified as individual reports to Takeda Pharmacovigilance.

Events/Issues which are not part of the study objectives and endpoints will not be abstracted or collected from healthcare records or other applicable source records.

Reporting of Adverse Drug Reactions to Regulatory Agencies and IRB/EC

LDRTC is responsible for reporting serious and non-serious adverse drug reactions suspected of being related to regulatory authorities. The Investigator is responsible for reporting adverse drug reactions to the IRB/EC, if required by national law or regulation, within the timelines required by such law or regulation. The Investigator shall maintain records of all such submissions.

Study-specific committees

No steering committee, data safety monitoring committee, or clinical endpoint committee will be used in this study.

STUDY OVERSIGHT

Premature Termination of Study:

[name], may prematurely terminate the study. Reasons for termination may include but is not limited to the following:

- Series of adverse events or incidences associated with subject participation.
- Low subject enrollment.

Clinical Research Quality Assurance:

To ensure that GCP and good clinical research are conducted per regulatory requirements and guidelines, the study will be made available for monitoring, auditing, review, and inspection by regulatory authorities such as IRB and FDA. This will be accomplished by providing direct access to study-related documents.

Data management

The acquired data will be entered into Excel for further analysis. Data will be analyzed using GraphPad Prism software (Graphpad Inc., La Jolla, CA) using ANOVA analysis and Student's t-test for statistical analysis. $p < 0.05$ is considered significant.

Samples and data storage

Once subjects have signed the informed consent form, they will be assigned a personal generic research study identification number. This number will be matched with the patient's name and demographic information in a file stored on a password-protected computer. Only members of the research team at **Lysosomal & Rare Disorders Research & Treatment Center, Inc** will have

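### Kidney involvement is defined by the current tests and only unadjusted tests are named, so a marker that merely tracks proteinuria can be identified and added value cannot be shown

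*Protocol*

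**What the plan says.** **Purpose.** The last paragraph of the opening background says that "this proposed study of pivotal urinary biomarkers may offer further insight on renal injury beyond current diagnostic tests". Study design and plan states without a hedge: "This prospective study aims to establish novel biomarkers for non-invasive detection of kidney involvement in FD".

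**Objective and aims.** The primary objective begins "Identify biomarkers in urine for the detection and progression of kidney involvement in naïve male and female patients with FD" and adds a comparison with patients on ERT. Aim 1 is "To identify urinary inflammatory biomarkers associated with nephropathy in FD". Aims 2 and 3 look at association with clinical urine markers, circulating lyso-Gb3 and kidney involvement, in naïve and in ERT-treated patients separately.

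**Comparison.** The text after Table 2 says "Urinary biomarkers will then be compared to the standard measures of kidney function and proteinuria" and lists GFR, microalbumin and UPCR among those measures. The text before Table 2 says that the common clinical markers "will be compared with the pivotal biomarkers associated with the inflammatory and dysregulated immune pathways".

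**Reference for kidney involvement.** Under Study population, the 5 patients without nephropathy are those with normal eGFR and no microalbuminuria. The 15 with nephropathy are divided by CKD stage. Study design and plan defines low renal involvement as UPCR of at most 0.5 g/g. No independent reference, such as histology, is named.

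**Analysis.** Data management says the data will be analysed "using ANOVA analysis and Student's t-test for statistical analysis", with p below 0.05 significant. No covariate is named.

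**The concern.** Albumin and UPCR are already non-invasive urine tests. A new urinary marker is of use beyond them only if it carries information they do not. A urinary cytokine can rise because a leaking kidney passes more protein of every kind. Such a marker will differ between patients with and without nephropathy, because albuminuria is part of how those groups are formed. It will also correlate with eGFR, because proteinuria does. An unadjusted t-test, ANOVA or simple association cannot separate this from a signal of the marker's own.

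At stake is how the results can be read. A marker with no information of its own can enter the list of identified markers, and the reader could not tell it from one that improves on tests patients already have.

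**Working it through.** The protocol gives no power calculation, effect size or correlation, so it has no figure to reproduce. The calculations below illustrate the size of the problem on assumed values.

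**Inputs from the protocol.** 25 Fabry patients, of whom 5 are naïve, which leaves about 20 on ERT (cohort 1 may mix the two). The nephropathy contrast is 5 without against 15 with. Alpha is 0.05, taken as two-sided.

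**Assumptions.** Marker M has correlation r with log UPCR (U), and eGFR (G) has correlation −ρ with U. Both r and ρ are set to 0.5, 0.6 and 0.7.

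**1. Albuminuria is built into the contrast.** Cohort 2a is nephropathy with CKD stage 1, which Table 3 gives as GFR above 90. Cohort 1 has normal eGFR and no microalbuminuria. Of the features that define cohort 1, only albuminuria can separate those 5 patients from it.

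**2. Marker that only tracks proteinuria, tested against eGFR.** M and G are independent given U, so corr(M,G) = −rρ, which is −0.25, −0.36 and −0.49. The unadjusted test is t = c√(n−2)/√(1−c²), with c the sample correlation. The adjusted test uses the partial correlation (c_MG − c_MU·c_GU)/√[(1−c_MU²)(1−c_GU²)] on n−3 degrees of freedom. Share of simulated studies with p < 0.05:

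| n | r=ρ=0.5 | 0.6 | 0.7 | adjusted for U |
|---|---|---|---|---|
| 25 (all Fabry) | 23% | 44% | 73% | about 5% |
| 20 (ERT) | 19% | 35% | 62% | about 5% |
| 5 (naïve) | 7% | 8% | 13% | about 5% |

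Simulation error is about one percentage point at most.

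**3. The same kind of marker in the 5 v 15 t-test.** Assume log albumin differs by 2 within-group SD. The marker then differs by 2r SD, and the noncentrality is 2r/√(1/5+1/15) = 2r/0.516 on 18 degrees of freedom:
- r = 0.5: noncentrality 1.94, significant in 45% of studies
- r = 0.6: 2.32, 59%
- r = 0.7: 2.71, 73%

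For separations of 1.5 to 3 SD and r from 0.3 to 0.7, the share runs from 13% to 97%. With log albumin as covariate it is about 5% throughout.

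**4. What adjustment costs a marker with its own effect.** Let G = −aU − 0.5M + error, with a = ρ − 0.5r so that corr(G,U) stays at −ρ. The unadjusted correlation is then, in size, rρ + 0.5(1−r²) = 0.625, 0.68 and 0.745. The partial correlation is 0.5√(1−r²)/√(1−ρ²) = 0.5 when r = ρ. Power:
- n = 25: about 73% adjusted, at least 94% unadjusted
- n = 20: about 62% adjusted, at least 87% unadjusted
- n = 5: about 9% adjusted

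The partial correlation detectable with 80% power is tanh[(1.960+0.842)/√(n−4)], which is 0.55 at n = 25, 0.60 at n = 20 and 0.99 at n = 5.

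**5. Limits of the adjusted test.** If inflammation lowers eGFR entirely through proteinuria, M and G are again independent given U, so a true signal is found in only about 5% of studies. If a single UPCR has reliability 0.7 (assumed), a marker of pure leak passes the adjusted test in about 7% to 19% of studies at n = 25.

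**The case against.** **No success rule is stated.** A reader might infer that markers succeed by agreeing with proteinuria and GFR, and that those which agree will be reported as going beyond current tests. The protocol says neither. It speaks of comparison and association. The phrase about current diagnostic tests is a hedged hope in the background, and the study calls itself descriptive and observational. This objection stands. The point concerns what the named analysis can support.

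**Other comparisons are planned.** A reader might also infer that agreement with standard measures is all that is examined. It is not: there are naïve v ERT, circulating lyso-Gb3, timing and duration of ERT (Aim 4), 25 healthy controls, a GFR-slope criterion and samples at 0, 6 and 12 months. A marker raised in cohort 1 over controls would be hard to put down to albumin leak, and the UPCR strata bear on the question too. This also stands, but cohort 1 has 5 patients, the strata are coarse, and no specified analysis is tied to these features or to the slope.

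**Adjustment belongs in a statistical analysis plan.** One may exist and may add it, so its absence alone is no finding. What the protocol does fix is a reference made from current tests, together with a named set of unadjusted tests.

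**Adjustment may mislead.** The rationale places podocyte injury and inflammatory pathways in the process that leads to glomerular damage, so proteinuria may be a mediator. Adjustment also costs power and is useless in 5 patients. All of this stands and limits what the adjusted result may be used to claim.

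**Conclusion.** The point holds in this form: kidney involvement is defined by the tests the study hopes to go beyond, and only unadjusted tests are named. A marker that merely tracks proteinuria can therefore be identified under Aim 1, and the named analysis cannot support an added-value statement.

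With assumed correlations of 0.5 to 0.7, such a marker reaches significance against eGFR in about 23% to 73% of studies at n = 25, and in the 5 v 15 contrast in 45% to 73% with a 2 SD albumin difference. Adjusted, both fall to about 5%. The sizes depend on those assumptions; the direction does not.

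The documents do not support reading this as a stated intention to present redundant markers as new. Nor would the adjusted analysis decide whether intrarenal inflammation is present.

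**What to change.** In all Fabry patients together, with ERT status noted, report each new marker's association with eGFR twice: alone, and with log UPCR or albumin from the same urine in the model. Give confidence intervals for both. Keep Aim 2, in the 5 naïve patients, descriptive.

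Fix the wording of conclusions in advance:
- Say that a marker carries information beyond proteinuria only if the adjusted association remains.
- Describe the others as not shown to add to proteinuria, not as disproved.
- Make no claim for or against intrarenal inflammation from the adjusted result alone, because proteinuria may be a mediator and a single UPCR is measured with error.

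Keep the unadjusted results as description.

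The cost is one regression per marker on data already planned, with no new samples. The real downside is power, so only strong independent signals will be found and fewer markers will be called novel.

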- 4) *Assess the role of the time of initiation and duration of therapy (ERT), respectively, inactivation and reversibility of inflammation cascade, and how these relate to the degree of kidney involvement in patients with FD.*

SUBJECT SELECTION

Number of Subjects

A total of 50 subjects, male or female, between the ages of 18 to 80 years of age, include 25 healthy individuals and 25 patients with Fabry disease.

Study population

FD patients n=25 (5 without clinical evidence of nephropathy and 15 patients with clinical evidence of nephropathy), NAÏVE FD patients (n=5), and healthy controls n=25 (controls, urine samples are not actual patients, urine samples will be purchased from a commercial company).

The study will involve 50 age-and gender-matched subjects and controls divided into the following cohorts:

1. FD subjects without clinical evidence of nephropathy (normal eGFR and no microalbuminuria) naïve or on ERT (**n=5**),
2. FD subjects with clinical evidence of nephropathy (**n=15**)
 Subcohorts:
 - a. FD subjects on ERT with CKD stage 1 (estimation n=5)
 - b. FD subjects on ERT with CKD stage 2 (estimation n=5)
 - c. FD subjects on ERT with CKD type 3 a or b (estimation n=5)
3. FD patients naïve to therapy (**n=5**). Can we be included in Cohort group 1 or 2.
 Additional analysis will be stratified NAÏVE vs. ERT.
4. Non-FD age-matched controls with no known kidney disease n=25.

	FD	Healthy control
Total FD	25	25
without nephropathy	5	
with nephropathy	15	
NAÏVE	5	

Table 3. Clinical staging of FD patients:

Clinical parameter(s)	FD patients and kidney involvement				Age-matched controls
	Stage 1	Stage 2	Stage 3a	Stage 3b	
Kidney involvement					
Kidney damage	Normal/	Mild reduction	Moderate reduction	Moderate reduction	normal
GFR ml/m1.73 m ²	>90	60-89	45-59	30-44	90 min
Cystatin-C	0.5-0.9	1.0-1.2	1.3-1.5	1.4-1.9	0.5-0.9
Urine B2M	-	0.428-0.603	0.603-0.950	0.950-1.034	-
FD biochemical markers					
α-Gal A	Deficiency	Deficiency	Deficiency	Deficiency	Normal
GLA mutations	Yes	yes	yes	yes	No
Gb-3	Yes	yes	yes	yes	No
Lyso-Gb-3	Yes	yes	yes	yes	No

Gender of Subjects

Subjects of both genders will be included in the research, and it is expected that this inclusion will be representative of the FD patients population.

Age of Subjects

Subjects will be between the age of 18 to 80 years of age.

Racial and Ethnic origin

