There are no enrollment restrictions based on race or ethnic origin, and it is expected that racial and ethnic representations in this study will represent the FD population.

INCLUSION/EXCLUSION CRITERIA

Inclusion criteria:

- a. Male and Female subject is greater than 18 but not older than 80 years.
- b. Subject willing to sign the informed consent and/or assent.
- c. Confirmed diagnosis of Fabry disease based on deficient α -Gal A enzymatic activity and molecular analysis demonstrating pathogenic variants in the *GLA* gene.

Exclusion criteria:

- a. Any other known genetic condition associated with CKD,
- b. Evidence of hepatitis B or C infections or other chronic infectious diseases,
- c. Pregnancy or breastfeeding.
- d. Any other chronic condition, as per PI's discretion, that makes the subject ineligible.

Description of criteria for withdrawal from the study

A subject may withdraw from the study at any time. The study is entirely voluntary.

RECRUITMENT:

Upon identifying patients with FD disease by the Principal Investigator, the research coordinator will recruit the study subjects. The research coordinator will recruit healthy controls in the clinic or purchase from a commercial company.

SETTING/LOCATION

Research subjects will be recruited at the **Lysosomal and Rare Disorders Research and Treatment Center, Inc (LDRTC)** located at [name], and/or [name].

Subjects recruited at these facilities will be receiving advice from [name], and be under her clinical care. All experimental/laboratory procedures will be performed by or under the supervision of [name]. All informed consent processes will take place at the indicated research sites.

Laboratory tests will be performed at **Lysosomal & Rare Disorders Research & Treatment Center, Inc**, whereas some assays such as Lyso-Gb3 will be performed outside collaborating laboratories such as Labcorp Diagnostic Laboratories and/or Centogene, Rostock, Germany.

STUDY PROCEDURES

Study type

Descriptive and observational study of molecular components detected in biological specimens of urine.

Study design and plan

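### The primary objective promises the effects of ERT from a naïve-versus-treated comparison in which ERT was not assigned, and the tests named carry no covariate

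*Protocol*

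**What the plan says.** Under *Objective and Specific Aims*, the primary objective is to find urinary biomarkers of kidney involvement in naïve men and women and then to "compare with patients on ERT to assess the effects of ERT". The rationale section also promises to analyse the role of therapy by setting stable-ERT patients against naïve ones. Aims 2 and 3 are worded as associations, one within naïve and one within ERT patients. Aim 4 turns to the timing and duration of ERT and the reversibility of inflammation.

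Under *Study Procedures, Study type*, the study is a "Descriptive and observational study of molecular components detected in biological specimens of urine".

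Under *Subject Selection, Study population*, there are 5 naïve patients. Three nephropathy subcohorts of about 5 each (CKD stages 1, 2 and 3) are all defined as on ERT. The 5 patients without nephropathy may be naïve or treated. For the contrast itself the section says "Additional analysis will be stratified NAÏVE vs. ERT". Age and gender matching is stated for subjects and controls.

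Under *Study Oversight, Data management*, data will be analysed "using ANOVA analysis and Student's t-test for statistical analysis", with p < 0.05 as significant. No covariate is named.

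**The concern.** An effect of ERT is the difference between what the same patients would show with and without it. Patients here are naïve or treated because of decisions made in routine care, and those decisions can depend on sex, age, disease course and kidney status. Each of these may also move urinary inflammatory markers. A plain comparison of means mixes such differences with any action of the drug.

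The protocol adds a visible link of its own. All the nephropathy subcohorts are on ERT, so treatment is tied to kidney severity by the way the cohorts are drawn up. The sentence on stratifying by naïve and ERT defines the contrast; it does not make the groups comparable.

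At stake is the interpretation of a primary objective. Read literally, a significant t-test would meet it and support a treatment-effect statement that the design cannot identify. Confounding could also hide a real difference.

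**Working it through.** The protocol gives no power, SD or effect size, so there is no figure of its own to reproduce. What follows shows how large the problem could be under assumed values.

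**Inputs from the protocol.** Naïve n = 5. On ERT: 3 × 5 = 15 from the nephropathy subcohorts, plus 0 to 5 from the mixed cohort without nephropathy, so 15 to 20. Student's t-test at 0.05 (two-sided assumed).

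**Assumptions.** True ERT effect zero. Sex difference in a marker 0.5 to 1.0 SD. Men: 20 to 40% of naïve, 60 to 80% of ERT patients.

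**Step 1: spurious difference from sex alone.** Difference = sex difference × difference in proportion male.
- Smallest: 0.5 × (0.60 − 0.40) = 0.10 SD.
- Largest: 1.0 × (0.80 − 0.20) = 0.60 SD.

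**Step 2: false-positive rate, 5 versus 20.** The standard error is √(1/5 + 1/20) = 0.50 SD. A noncentral t with 23 df gives 5.4% at a shift of 0.10 SD and 21.0% at 0.60 SD (noncentrality 0.60/0.50 = 1.2). That calculation takes the within-group SD as 1 and so omits the variance that a mixture of sexes adds. With 1 of 5 and 16 of 20 men and a 1.0 SD sex difference, the added sum of squares is 5 × 0.2 × 0.8 + 20 × 0.8 × 0.2 = 4.0. On 23 df this raises the pooled variance from 1 to about 1.17. Simulating with fixed sex counts and a within-sex SD of 1 gives:

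| Men, naïve vs ERT | Sex difference 0.5 SD | Sex difference 1.0 SD |
|---|---|---|
| 2/5 vs 12/20 | 4.8% | 4.0% |
| 1/5 vs 16/20 | 8.2% | 16.8% |

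The range is about 4 to 17%.

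**Step 3: kidney severity.** Code no nephropathy as 0 and CKD stages as 1 to 3, and let a marker rise by b SD per stage with no ERT effect. The mean stage is (5×1 + 5×2 + 5×3)/15 = 2.0 for 15 ERT patients and 30/20 = 1.5 for 20. The naïve case-mix is unknown. Two assumed mixes:

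| Naïve stages (mean) | ERT n | Spurious difference | Rejection at b = 0.5 | Rejection at b = 1 |
|---|---|---|---|---|
| 0,0,0,1,1 (0.4) | 15 | 1.6b | 26% | 66% |
| 0,0,0,1,1 (0.4) | 20 | 1.1b | 12% | 23% |
| 0,1,1,2,3 (1.4) | 15 | 0.6b | 6% | 6% |
| 0,1,1,2,3 (1.4) | 20 | 0.1b | 3% | 0.3% |

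The result depends almost wholly on who the 5 naïve patients turn out to be. With a similar case-mix there is no excess of false positives.

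**Step 4: what adjustment can do.** Adding a correctly specified linear stage term returns the rejection rate to about 5% and the mean estimate to about 0 in every scenario. The standard error of the adjusted difference is 0.50 to 0.70 SD. The 95% half-width is then about 2.07 × 0.50 = 1.0 SD (22 df) to 2.11 × 0.70 = 1.5 SD (17 df). Even unadjusted, 80% power needs a true difference of 1.46 SD (5 versus 20) to 1.53 SD (5 versus 15).

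**The case against.** The strongest reply is that this is loose phrasing in one clause. The study calls itself descriptive, aims 2 and 3 speak of associations, naïve versus ERT is labelled an additional analysis, and the stated use of the data is to understand renal function better. The sentence on statistics sits under data management and names families of tests. It does not rule out further factors, ANOVA can carry them, and an SAP may add covariates. The protocol also records disease and ERT history, ACE inhibitor and ARB use, antibody status, CKD stage and UPCR.

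Much of this stands. The absence of a covariate list is not an error in itself, since an SAP could supply one. A reader might infer that the study will report case-mix as a drug effect. The protocol does not say so, and that would be a forecast. A reader might also take the 21% from the simple noncentral t, or higher figures obtained by positing a total bias of 0.8 to 1.0 SD, as the expected error rate. The first overstates the sex illustration, and the second rests on a bias that no figure in the protocol supports.

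What the reply does not remove is the wording. The primary objective states a causal purpose, aim 4 leans the same way, and an SAP would inherit both.

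**Conclusion.** The point holds as one about wording and interpretation. The primary objective asks an unassigned, unmatched comparison of 5 naïve with 15 to 20 treated patients for the effects of ERT, and the tests named cannot separate ERT from the reasons for treatment. The risk is clear from the design; its size and direction are not. Under the assumed sex mix the false-positive rate runs from about 4% to about 17%. Under assumed kidney case-mixes it runs from no excess to well above that. None of these sex mixes, marker differences or naïve case-mixes comes from the protocol.

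It would also be too strong to conclude that adjusting for age and sex cures the problem. Such a model leaves kidney severity untouched, and no model of recorded covariates removes unmeasured confounding. The rewording has to carry most of the repair. This should be changed, but it does not undermine the biomarker description that is the rest of the objective.

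**What to change.** 1. Reword the second half of the primary objective: describe differences in urinary markers between naïve patients and patients on ERT, in line with the association wording of aims 2 and 3. Add that no causal effect of ERT will be concluded.
2. For this contrast, report the unadjusted difference with a 95% confidence interval beside the estimate from a linear model with age and sex.
3. Add a sensitivity analysis that also includes kidney status (CKD stage, or eGFR and UPCR). It is better as a sensitivity analysis because kidney status may itself be partly a result of treatment, and because few naïve patients are available to support the extra terms.

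The cost is small: one changed sentence and two models on data already planned for collection, with no change to visits, samples or care. The downside is a few degrees of freedom, a wider interval with only 5 naïve patients, and a more modest claim. Residual confounding remains and should be stated with the results.
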